9.5 Safety assessment

The investigator or qualified designated staff will assess adverse events in every subject during the study, and the follow-up period according to the trial schedule and adverse events will be graded and recorded according to CTCAE v4.03. The characteristics of the adverse event will be determined based on the following aspects: severity, causality, toxicity grade, and measures adopted for the investigational treatment.

All AEs with an unknown etiology that occur during the study must be assessed to determine whether it is an irAE.

9.5.1 Definition of adverse events

Adverse event (AE): An adverse event refers to any untoward medical event that occurs in a clinical trial subject after receiving a drug and does not necessarily have a causal relationship with the treatment. Any untoward medical event from the moment the subject signed the informed consent form and received the investigational drug to 1 month after the treatment has ended is considered an AE, regardless of whether it has a causal relationship with the investigational drug.

Serious adverse event (SAE): refers to an AE that occurs at any dose of the investigational drug or at any time during the observation period that requires hospitalization, prolongation of hospitalization, permanent or serious disability or causing life-threatening events, death, a congenital anomaly or deformity.

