Hepatitis B, hepatitis C test ¹⁰	X				If positive, hepatitis B DNA and hepatitis C RNA will be measured on d1 ± 7d in every 2 cycles					
HIV test ¹⁰	X									
Pregnancy test ¹¹	X									

12-lead electrocardiogram		X			X			X	X	
Clinical evaluation examination										
ECOG scoring	X				X					
Evaluation of adverse events ¹²	From the signing of the informed consent form to 30 days after the last dose									
Quality of life questionnaire ¹³		X			X ⁸				X	
Administration of investigational product										
IBI308 administration		X			X					
Anlotinib administration	Administration is recorded daily on d1–d14 of every treatment cycle									
Efficacy evaluation										
Radiologic tumor evaluation ¹⁴	X	Evaluation is performed once after the 2nd treatment cycle (C3) and once after the 4th treatment cycle (C5). Subsequently, an evaluation will be performed once after the 7th cycle (C8) and once after the 10th cycle (C11). After the 10th cycle, an evaluation will be performed once every 4 treatment cycles, and the time window for radiological evaluation is ± 7 days.								
Follow-up after treatment has ended										

Progressive disease	Radiologic evaluation is performed every 3 months after the last dose until disease progression						
Biomarker exploration							
Biomarker blood sampling/sample collection	X						

1. The informed consent form should be signed by subjects before any procedures outlined in the protocol.
2. Vital signs include body temperature, pulse, respiratory rate, and blood pressure.
3. Height is only measured during the screening period. Weight is measured before every dose, except for physical examination during the screening period; physical examination abnormalities during the trial only need to be recorded in the CRF.
4. Routine blood tests include RBC, HGB, HCT, WBC, PLT, and white blood cell categories [LYM, ANC, MONO, EOS, BASO].
5. Blood chemistry includes liver function tests [TBIL, ALT, AST, γ -GT, ALP, ALB, TP, LDH], renal function tests [UREA, Cr], blood electrolytes [Na, K, Cl, Mg], amylase, lipase, blood lipids [total cholesterol (CHO), triglycerides (TG), high-density lipoprotein cholesterol, low-density lipoprotein cholesterol], and fasting blood glucose.
6. Routine urine tests include UWBC, UPRO, URBC, UGLU. Any subjects with $\geq 2+$ proteinuria in routine urine tests must undergo 24-hour urine protein quantification during the screening period.
7. Routine stool test should include stool routine.

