1.6 Background of the investigational drugs

IBI308 is an IgG4 monoclonal antibody that can specifically bind to PD-1 molecules on the surface of lymphocytes, blocking the PD-1/programmed cell death-1 ligand-1 (PD-L1) pathway that results in tumor immune tolerance and reactivating antitumor activity of lymphocytes to achieve tumor treatment. IBI308, nivolumab, and pembrolizumab all have the same target but different amino acid sequences. A phase Ia pharmacokinetics study in patients with advanced solid tumors found that increased *in vivo* exposure to sintilimab is almost proportional to a dose increase in the 1–10 mg/kg range, suggesting linear pharmacokinetics. After a single dose of sintilimab was administered to subjects with solid tumors, the clearance half-life (Geo.Mean [CV%]) was 14.4 [28.9%] days, the clearance rate 11.5[42.5%]mL/h, the steady-state volume distribution 5.43[34.4%]L and the apparent volume distribution 5.77[33.2%]L, with PK characteristics similar to other anti-PD-1 antibodies already on the market (nivolumab and pembrolizumab). The efficacy data of IBI308 come mostly from a phase II key single-arm study (ORIENT-1) of IBI308 monotherapy in the treatment of recurrent or refractory classical Hodgkin lymphoma. Ninety-six patients were enrolled in ORIENT-1, the ORR of the per-protocol set was 65.5%, and the 97% CI was 50.5%–78.6%, which was consistent with the results of the efficacy analysis. Phase III studies on sintilimab have been conducted in several solid tumors, including non-small-cell lung cancer (ORIENT-12).

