2.2 Secondary objectives

- To assess the duration of response (DoR) of IBI308 combined with anlotinib for recurrent/advanced endometrial cancer based on irRECIST and RECIST (1.1) criteria.
- To assess the disease control rate (DCR) of IBI308 combined with anlotinib for recurrent/advanced endometrial cancer based on irRECIST and RECIST (1.1) criteria.
- To assess the time to objective response (TTR) of IBI308 combined with anlotinib for recurrent/advanced endometrial cancer based on irRECIST and RECIST (1.1) criteria.
- To assess the progression-free survival (PFS) of IBI308 combined with anlotinib for recurrent/advanced endometrial cancer based on irRECIST and RECIST (1.1) criteria.
- To assess overall survival (OS) of IBI308 combined with anlotinib for recurrent/advanced endometrial cancer based on irRECIST and RECIST (1.1) criteria.
- To assess the 12-month OS rate of IBI308 combined with anlotinib for recurrent/advanced endometrial cancer based on irRECIST and RECIST (1.1) criteria.
- The incidence of adverse events and serious adverse reactions.

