6.1. Overall principles

Dose modification must be based on the most severe drug toxicity that occurred in the previous dosing cycle. Three days before each dosing of the investigational drug on Day 1, the blood, liver, and renal function test results of the subject must meet the dosing requirements. All other toxicities must be resolved to CTCAE v4.03 Grade 0–1 or baseline

level (except for alopecia, fatigue, special regulations in the protocol, or other conditions that are deemed not clinically significant by the investigator). If the subject is not dosed as scheduled due to drug toxicity, the next dose can be delayed. If an investigational drug needs to be suspended/permanently discontinued due to investigational drug-related toxicity or other reasons, other investigational drug(s) can be used independently if the corresponding criteria are met. All dose modifications must be recorded in the file, including the reason and management.

AEs related to sintilimab exposure may stem from immunological etiologies. These immune-related AEs (irAEs) may occur within a short period after the first dose or several months after the last dose of sintilimab. They may affect more than one system simultaneously. Based on existing clinical trial data, most irAEs are reversible and can be managed by drug dosing interruption, administration of glucocorticoids, and/or other supportive treatments. For suspected irAEs, an appropriate evaluation must be performed to confirm the etiology or rule out other causes. Other procedures or tests, such as bronchoscopy, endoscopy, or skin biopsy, can be included in this evaluation. Sintilimab will be suspended or permanently discontinued, and glucocorticoids will be administered based on irAE severity. For dose modification and toxicity management guidelines for potential irAE, please refer to the “Management manual for immune-related adverse event” provided by the pharmaceutical company.

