8.3 Safety visit

8.4 The safety follow-up is performed 30 ± 3 days after the last dose or before new antineoplastic therapies. The safety visit includes the following activities: Recording of vital signs, weight, physical examination, ECOG-PS score, 12-lead electrocardiography, routine blood/blood chemistry/urine results, coagulation function results, thyroid function, adverse event evaluation, concomitant medications, and subsequent antineoplastic treatment (if applicable).

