8.5 Survival visit

An outpatient or telephone follow-up will be performed 1 month after the last dose for every subject; adverse events and concomitant medications within 1 month of the end of treatment will be recorded. Subsequent follow-up on overall evaluation data will be performed until disease progression or new antineoplastic treatment starts. Subsequent antineoplastic treatment and its start date will be recorded, and survival follow-up will be performed.

If the subject withdraws from the study due to toxicity symptoms, withdrawal of informed consent, and disease progression, it will be considered the end of treatment. The reason for treatment discontinuation, the treatment end date, and the withdrawal date will be recorded. At the end of treatment, adverse reactions and concomitant treatments within 30 days after the last dose of the investigational drug will be collected.

9. Efficacy Evaluation

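### Adverse events are counted only if they begin within 30 days of stopping treatment, so the later immune-related events that the protocol says may occur are left out of the safety incidence

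*Protocol*

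**What the plan says.** Section 2.2 lists among the secondary objectives "The incidence of adverse events and serious adverse reactions". The period over which events are collected is set in four places:

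- Section 9.5.1 (definition): events count from consent and first drug "to 1 month after the treatment has ended is considered an AE".
- Table 1, adverse-event row: "From the signing of the informed consent form to 30 days after the last dose".
- Section 8.5, post-treatment contact: "adverse events and concomitant medications within 1 month of the end of treatment will be recorded".
- Section 8.5, end of treatment: adverse reactions "within 30 days after the last dose of the investigational drug will be collected".

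The section headed 8.3 Safety visit times the visit: "The safety follow-up is performed 30 ± 3 days after the last dose or before new antineoplastic therapies".

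Section 6.1 describes the toxicity itself. Immune-related events "may occur within a short period after the first dose or several months after the last dose of sintilimab". Section 9.5 asks that every event of unknown cause during the study be assessed as a possible immune-related event. Table 1 provides a survival visit every 3 months but marks no adverse-event assessment, laboratory test or ECG there.

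**The concern.** The protocol recognises a class of toxicity that can begin months after the last sintilimab dose, makes the incidence of adverse events an objective, and then defines late onsets out of the count. A pneumonitis or hepatitis that first appears in week 8 after the last dose is not an adverse event of this trial under section 9.5.1. The SAE definition is built on the adverse-event definition, so it offers no clearly longer window.

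At stake is how completely the safety profile of a new combination is described. Late onsets can only be lost, never gained, so the direction of the error is known. An analysis plan cannot repair this, because events that were never collected cannot be analysed. Some of the lost events would be readily attributable: the synopsis allows treatment to stop for complete response after 6 cycles, or after 2 years of anti-PD-1 treatment, and such patients may go some time without another therapy.

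**Working it through.** **Step 1: is the window consistent?** Section 9.5.1, Table 1 and both statements in section 8.5 give 30 days or one month. They agree on length. They differ on the starting point: end of treatment in 9.5.1 and the first statement of 8.5, last dose in Table 1, and last dose of the investigational drug in the second statement of 8.5. Section 6.1 allows one drug to continue after the other is stopped, and section 5.2 caps sintilimab at 24 months while anlotinib runs until progression or intolerance. No passage says which drug's last dose starts the clock.

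**Step 2: does any other text capture a new onset after the window?**

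- Section 9.5 mentions the follow-up period, but ties assessment to the trial schedule, which in Table 1 ends at 30 days.
- Section 9.5.4 has events followed to resolution. That covers events already recorded, not new ones.
- The SAE definition in 9.5.1 refers to an observation period that is not defined, and it applies to what is already an adverse event.
- The survival visit in Table 1 carries no adverse-event enquiry.

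Nothing extends the onset window for immune-related events or SAEs.

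**Step 3: set against section 6.1.** The stated latency is up to several months after the last sintilimab dose, and collection ends at one month. The interval between the two is uncovered.

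**Step 4: size.** The protocol states no proportion of patients with a first immune-related event after day 30, so there is no figure to reproduce. Two things can be shown.

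- Weight of one patient, with the planned 23 patients (section 3.1): 1/23 = 4.3 percentage points.
- A range under assumed late-onset proportions q, which are not in the protocol. Expected patients missed = 23q; chance of missing at least one = 1 − (1 − q)^23.

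| Assumed q | Expected missed | Chance of at least one |
|---|---|---|
| 2% | 0.5 | 37% |
| 5% | 1.2 | 69% |
| 10% | 2.3 | 91% |
| 15% | 3.5 | 98% |

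**Step 5: background on exposure.** Section 1.6 reports that after a single dose "the clearance half-life (Geo.Mean [CV%]) was 14.4 [28.9%] days". Taking the fraction remaining as 0.5^(t/14.4), day 30 is 30/14.4 = 2.1 half-lives with about 24% remaining, and day 90 is 90/14.4 = 6.25 half-lives with about 1.3% remaining. This shows that drug is still present when collection stops. It does not measure how many events are missed.

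**The case against.** The strongest reply is that this is a declared design choice. The 30-day length is the same wherever it appears, section 6.1 is a toxicity-management statement about what may happen and promises no late collection, and an incidence within a stated window is a correct estimate for that window. That is fair as far as it goes: the error exists only relative to an incidence meant to include late onsets. But section 2.2 names the incidence without limiting it to 30 days, and a reader of the results would not know that a toxicity described in section 6.1 had been left out by definition. Stating the limit would answer the interpretive point, though it would not recover the events.

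Three stronger readings are tempting, and the documents do not support them.

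- A reader might infer that patients who stop early for toxicity have their whole off-drug period outside collection. They do not: the first 30 days are inside, the event that led to stopping is followed to resolution, and where anlotinib continues alone the window may run longer after the last sintilimab dose. Nothing shows that the loss is greatest in this group.
- A reader might infer from the safety-visit wording that collection closes even earlier when new therapy starts. That sentence moves the visit; it does not shorten the window set in 9.5.1, 8.5 and Table 1.
- A reader might take the residual drug percentages as the size of the undercount. No passage links serum concentration to the onset of immune-related events.

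**Conclusion.** The gap is real and follows from the text alone: an immune-related event that first appears after the 30-day window is not counted, although section 6.1 says such events may occur. Reported incidence of immune-related events and related SAEs can only be too low for late onsets. The magnitude cannot be derived from the protocol. The table above rests on assumed late-onset proportions, and the only firm figure is that one missed patient in 23 is worth 4.3 points. The point concerns new onsets only. The ORR endpoint, the sample size and the stopping rule do not depend on it. The conclusion assumes that no wider enquiry is made at survival visits than Table 1 shows.

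**What to change.** In section 9.5.1, section 8.5 and the adverse-event row of Table 1:

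- Keep 30 days for all adverse events.
- Extend collection of immune-related events, and of SAEs not judged possibly or definitely unrelated, through the first 3-monthly survival visit, about 90 days after the last sintilimab dose, whether or not new therapy has started. In the categories of section 9.5.3 those SAEs are the definitely related, possibly related and not assessable ones. The last category matters because it covers reactions with unclear timing that resemble a known drug effect.
- State which drug's last dose starts each window.
- Use the start date of new therapy, which section 8.5 already requires, when judging attribution.
- Tabulate late events separately in the safety tables.
- Report that immune-related incidence covers onset up to this limit. Several months may exceed 90 days, and late events without symptoms may still be missed, because no laboratory tests are scheduled at survival visits.

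The cost is a protocol amendment and a few added case report form questions at a contact that already takes place. The downside is that some late events will be confounded by subsequent therapy, and the rates may look slightly less favourable.

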9.5.2. Adverse event determination criteria

Adverse reactions should be assessed based on the Common Terminology Criteria for AEs (NCI CTCAE v4.03 grading criteria). The following criteria can be used to assess AEs that are not listed in the NCI toxicity grading criteria:

- Grade 1 (mild): the presence of discomfort that does not affect normal daily activities;
- Grade 2 (moderate): severity of discomfort insufficient to decrease or affect normal daily activities;
- Grade 3 (severe): Unable to work or carry out normal daily activities;
- Grade 4 (fatal): results in disability or death.

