6.2. IBI308 (sintilimab) dose modification

Sintilimab dose modification is not permitted during the entire study. Table 3 shows the principles of suspension and permanent discontinuation for sintilimab. If the dose delay occurs during sintilimab treatment (3 weeks per cycle), all future dosing dates will be delayed to ensure that the dosing interval between sintilimab treatment cycles is 21 ± 3 days.

Table 2. Dose modification protocol for IBI308 (sintilimab)-related toxicity

Sintilimab-related adverse events	Severity	Dose modification
Hematological toxicity	Grade 1–3	Drug discontinuation not required
	Grade 4	Drug interruption
Pneumonitis	Grade 2 pneumonitis	Drug interruption
	Recurrent Grade 2 to Grade 4 pneumonitis	Permanent drug discontinuation
Diarrhea/enterocolitis	Grade 2 or 3 diarrhea or enterocolitis	Drug interruption

	Grade 4 diarrhea or enterocolitis	Permanent drug discontinuation
Dermatitis	Grade 3 dermatitis	Drug interruption
	Grade 3–4 dermatitis	Permanent drug discontinuation
Impaired hepatic function	Grade 2 AST, ALT, or TBIL increased in subjects with normal baseline AST, ALT, or TBIL; $\geq 50\%$ increase in AST, ALT, or TBIL (reaching grade 2 requirement) lasting < 7 days in subjects with baseline AST, ALT, or TBIL $> \text{ULN}$.	Drug interruption
	Grade 3 or 4 AST, ALT, or TBIL increased in subjects with normal baseline AST, ALT, or TBIL; $\geq 50\%$ increase in AST, ALT, or TBIL (reaching grade 3 or 4 requirements) lasting ≥ 7 days in subjects with baseline AST, ALT, or TBIL $> \text{ULN}$.	Permanent drug discontinuation
Hypophysitis	Grade 2 hypophysitis	Drug interruption
	Grade 3–4 hypophysitis	Permanent drug discontinuation
Adrenal insufficiency	Grade 2 adrenal insufficiency	Drug interruption
	Grade 3 or 4 adrenal insufficiency	Permanent drug discontinuation
Hyperthyroidism	Grade 3–4 hyperthyroidism	Permanent drug discontinuation
Hyperglycemia	Grade 3 hyperglycemia	Drug interruption
	Grade 4 hyperglycemia	Permanent drug discontinuation
Renal impairment	Grade 2–3 increase of creatinine	Drug interruption
	Grade 4 increase of creatinine	Permanent drug discontinuation
Neurotoxicity	Grade 2 neurotoxicity	Drug interruption
	Grade 3–4 neurotoxicity	Permanent drug discontinuation
Other AEs	First occurrence of other Grade 3 AE	Drug interruption
	Second occurrence of the same Grade 3 AE	Permanent drug discontinuation

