
Grade 3: Long duration (rapid response does not occur even after symptomatic treatment and/or temporary interruption of infusion); symptoms recur after initial improvement; inpatient treatment is required due to other clinical sequelae (such as kidney injury, lung infiltration) Grade 4: Life-threatening, vasopressor or ventilator support indicated
	
Stop infusion Other appropriate drug treatments may include but are not limited to: Adrenaline**, intravenous infusion, antihistamines, NSAIDs, paracetamol, anesthesia, Oxygen, vasopressor, corticosteroids. Strengthen monitoring of vital signs based on the medical indications of the patient until the investigator deems that the subject's condition is stable. Inpatient treatment may be indicated. **Adrenaline must be immediately administered if anaphylaxis occurs. Further investigational drug treatment will be permanently discontinued.
	
No subsequent treatment

The ward should be equipped with appropriate resuscitation equipment, and the physician should be contactable at any time during the dosing period. For further information, please refer to the Common Terminology Criteria for Adverse Events (CTCAE v4.03)(http://ctep.cancer.gov)
		

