ms). In patients on anlotinib who take antiarrhythmic drugs or have related underlying heart disease, bradycardia, and electrolyte disturbance, electrocardiography should be performed every 2–3 weeks to evaluate the QT interval.

Electrocardiography and cardiac function should be closely monitored during the dosing period. Drug interruption is recommended if a Grade 3/4 adverse reaction occurs. If a Grade 3/4 adverse reaction recurs after dosing is resumed, subsequent doses can be reduced by one level. Drug discontinuation is recommended if the adverse reaction persists. Drug discontinuation is recommended for patients who develop Grade III–IV heart failure or patients with a left ventricular ejection fraction <50% on Doppler echocardiography.

Stroke risk: Although a stroke event has yet to be observed in existing clinical trials of anlotinib, hypertension and hyperlipidemia are common adverse reactions of anlotinib and constitute a high-risk factor for stroke. Long-term use of this product may increase stroke risk. Therefore, it is recommended that blood pressure, blood lipids, and other stroke risk factors should be closely monitored in high-risk stroke patients to prevent stroke.

Epilepsy: Epilepsy was observed in patients in the anlotinib arm in clinical trials. It has not been confirmed whether this product can cause epilepsy or increase the risk of epilepsy. This product should be used with caution under the guidance of a physician for patients with a medical history of epilepsy.

Dermatotoxicity: Hand-foot-skin reaction (swelling and pain in the palms and soles or erythema of the fingers and toes) is a common adverse skin reaction with this type of drug. A Grade 1 hand-foot-skin reaction is characterized by painless mild skin changes or dermatitis (e.g., erythema, edema, hyperkeratosis); a Grade 2 hand-foot-skin reaction is characterized by painful skin changes (e.g., desquamation, blisters, bleeding, swelling, and hyperkeratosis) and affects instrumental activities of daily living; a Grade 3 hand-foot-skin reaction is characterized by severe skin changes (e.g., desquamation, blisters, bleeding, swelling and hyperkeratosis) and accompanied by pain, which affects activities of daily living.

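### The fallback severity scale for adverse events outside CTCAE does not separate Grade 1 from Grade 2, leaves activity-limiting events ungraded, and has no place for survived life-threatening events

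*Protocol*

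**What the plan says.** Section 9.5.2 of the protocol makes CTCAE v4.03 the governing scale and adds a residual one: "The following criteria can be used to assess AEs that are not listed in the NCI toxicity grading criteria". It has four levels:

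- The lowest level is worded "Grade 1 (mild): the presence of discomfort that does not affect normal daily activities".
- The next level up is worded "Grade 2 (moderate): severity of discomfort insufficient to decrease or affect normal daily activities".
- The third level is worded "Grade 3 (severe): Unable to work or carry out normal daily activities".
- The highest level is worded "Grade 4 (fatal): results in disability or death".

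Other sections give these grades different content. The infusion-reaction table in section 6.3 has "Grade 4: Life-threatening, vasopressor or ventilator support indicated". Section 6.5 describes a Grade 2 hand-foot-skin reaction as one that "affects instrumental activities of daily living". The definition of a serious adverse event in section 9.5.1 names disability, threat to life and death as separate criteria.

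Grades also drive treatment rules that reach unlisted events. In section 6.2, the sintilimab rows for other AEs distinguish "First occurrence of other Grade 3 AE" (interruption) from a Grade 4 event (permanent discontinuation). They also require permanent discontinuation when a Grade 3 event has not come down to Grade 0–2 or baseline by 7 days, or to Grade 0–1 or baseline by 14 days. In section 6.4, the general anlotinib rule for Grades 3 and 4 holds the drug until the reaction is below Grade 2.

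**The concern.** A severity scale has to place every event in exactly one level. This one appears to put some events in two levels and others in none. It is also the only written definition that the protocol supplies where CTCAE gives no grade.

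Two things are at stake. First, the rules in sections 6.2 and 6.4 take the grade as input, so an undefined boundary leaves the investigator to guess which row or recovery threshold applies. Second, the incidence of adverse events is a secondary objective (section 2.2) and events are graded and recorded (section 9.5, safety assessment). Grades assigned on this scale would sit in the same dataset as CTCAE grades without meaning the same thing.

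**Working it through.** No arithmetic applies. The check takes six kinds of event not listed in CTCAE and applies the four written levels literally.

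| Event | Level met in section 9.5.2 |
|---|---|
| (a) Discomfort, daily activities unaffected | Grade 1 and Grade 2 |
| (b) Daily activities reduced but not prevented | None: more than Grade 2 as written, less than Grade 3 |
| (c) Work or daily activities impossible | Grade 3 |
| (d) Life-threatening, survived without disability | Not Grade 4; Grade 3 at most |
| (e) Disabling, survived | Grade 4, although that level is headed fatal |
| (f) Death | Grade 4, the same as (e) |

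Only (c) is placed cleanly. For (a), nothing but the labels mild and moderate separates the two levels.

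**Against the rest of the protocol.** The hand-foot-skin definition in section 6.5 has Grade 2 affecting instrumental daily activities; fallback Grade 2 requires that activities are not affected. The infusion-reaction table in section 6.3 puts threat to life at Grade 4; the fallback scale has no level for it. Section 9.5.1 keeps threat to life, disability and death apart; section 9.5.2, immediately after it, drops the first and merges the other two.

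**Through the rules that use grade, for an unlisted event.**

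1. *Sintilimab recovery thresholds (section 6.2).* Suppose a Grade 3 event improves to state (b). It then has no grade, so whether the 7-day threshold of Grade 0–2 is met cannot be read off. Suppose it improves to state (a). It is then Grade 1 or Grade 2 by label alone, so whether the 14-day threshold of Grade 0–1 is met is equally undetermined.
2. *Anlotinib general rule (section 6.4).* The Grade 3 and Grade 4 rows share the threshold of below Grade 2. This depends on the same Grade 1/2 boundary.
3. *Sintilimab Grade 3 versus Grade 4 rows for other AEs (section 6.2).* Event (d) cannot reach the Grade 4 row on the fallback scale. It can at most reach the Grade 3 rows, although the same description counts as Grade 4 in section 6.3.

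**The case against.** The strongest reply is that little turns on this, and much of that reply stands.

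- **Scope.** CTCAE v4.03 governs. The fallback is worded permissively and covers only what CTCAE does not list. The infusion reactions in section 6.3 and the hand-foot-skin reaction in section 6.5 have their own grade definitions and are never graded on it. Those comparisons show that the fallback wording is out of line with the protocol's own usage; they do not show that one event falls under two conflicting rules.
- **Life-threatening events.** A reader might infer that a patient with event (d) would only have sintilimab interrupted. The documents do not support that. Section 9.5.1 makes a life-threatening event serious whatever its grade, and section 4.4 lists serious adverse events among the reasons for withdrawal. The synopsis list of withdrawal criteria omits serious adverse events, but that is a separate inconsistency.
- **Anlotinib Grade 4 row.** A reader might infer that interruption and dose reduction after Grade 4 is impossible because the fallback Grade 4 is fatal. That goes too far: the level also includes disability, and a disabling event can be survived.
- **Grade tables.** A reader might infer that the trial's safety tables by grade would be wrong. The protocol specifies no such table. The synopsis promises descriptive methods and percentages, and section 11.2 sets out no adverse-event table by grade.
- **Grade 2 as a trigger.** For unlisted events, neither the other-AE rows in section 6.2 nor the general rule in section 6.4 starts an action at Grade 2. The Grade 1/2 overlap acts through recovery thresholds only. The redosing threshold in section 6.1 is expressed in CTCAE grades, so it is not relied on here.

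The word insufficient in Grade 2 may be a translation slip. That would explain the overlap without curing it, and it would not explain Grade 4.

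**Conclusion.** The point holds as a definite wording defect with a narrow effect. Grades 1 and 2 share one functional criterion, activity-limiting events have no grade, and Grade 4 omits survived life-threatening events while merging disability with death. For events outside CTCAE, the recovery thresholds in sections 6.2 and 6.4 and the Grade 3 versus Grade 4 rows in section 6.2 cannot be applied consistently, and the recorded grades are not comparable with CTCAE grades.

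The size cannot be put in numbers, because the protocol gives no expected count of unlisted events; there may be few. The response endpoint, the sample size and the stage 1 decision are unaffected. The conclusion assumes that the scale is read as written and is actually used when CTCAE gives no grade. The broader reading, that unlisted events will routinely be mis-graded and the safety rules will misfire, is not supported: use of the scale is optional, and section 4.4 acts on serious events independently of grade.

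**What to change.** Reword section 9.5.2 so that:

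- Grade 2 is distinct from Grade 1 and covers discomfort that reduces daily activities without preventing them;
- life-threatening non-fatal events and death each have a defined place, consistent with the CTCAE v4.03 grades used elsewhere in the protocol.

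Moving life-threatening events on the scale changes which unlisted events reach which row of section 6.2, so the rewording has treatment consequences. The sponsor should therefore reconcile the new scale with the grade-based rules in sections 6.2 and 6.4 and with the withdrawal criteria in section 4.4. Which action belongs to which grade is for the sponsor to decide, and none is proposed here.

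The cost is a few lines of protocol text and a matching note on completing the case report form. No additional data are needed.
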